10.2.3 Data Safety Monitoring Board

A DSMB will oversee the study to ensure patient safety and to advise if any dosing alterations are recommended. The DSMB will review safety including thyroid hormone effects, liver-related events (ie, clinically meaningful elevations in liver enzymes ALT, AST, and bilirubin), and other efficacy (lipid parameters) and safety data as needed. The DSMB will perform regularly scheduled reviews as well as an additional review if necessary.

10.2.4 Sample Size Determination

Up to 105 patients in total will be randomized to 1 of 2 treatments (70 patient to MGL-3196, 35 patients to placebo). It is estimated that the treatment difference of percent change in LDL-C from baseline to Week 12 between any dose of the MGL-3196 group and the placebo group is about -20%. With a common standard deviation for the change in LDL-C at 20%, 27 patients per group to complete the Week 12 visit will provide 90% power with a two-sample t-test. The significance level is set as 0.025 for the consideration of multiplicity in comparisons of 2 daily dosing regimens of MGL-3196 vs. placebo group. The enrollment size is designed to allow for dropouts before the 12-week visit, and as such, patients who drop out of the study will not be replaced.

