MGL-3196-06 employs a simple adaptive design, that will optimize dose for individuals randomized to MGL-3196. Based on studies in 129 individuals safely dosed for up to two weeks with MGL-3196, at doses ranging from 50- 200 mg per day, MGL-3196 drug exposure shows variability in exposure between individuals and higher exposure in some individuals, particularly at the 200 mg dose, which will not be used in the Phase 2 HeFH study. This is similar to statins, which are also liver-directed drugs that interact with liver and gut uptake transporters. MGL-3196 exposures are less variable at the lower doses, including 60-100 mg, that will be studied in this Phase 2 study. There are no studies that suggest that exposure to MGL-3196 will be different in patients with HeFH or that HeFH patients have consistent alterations in drug metabolizing enzymes or transporters which may be involved in MGL-3196 uptake by the gut or liver. Unlike statins, there has been no myopathy associated with higher drug exposures of MGL-3196 in humans or animal studies; nonetheless, the design of the HeFH Phase 2 trial is adaptive in that

dose adjustments of MGL-3196 will be made after 2 weeks of dosing to optimize exposure for the individual patient.

MGL-3106 exposure variability, which may relate to polymorphisms in drug metabolizing enzymes and transporters, may occur in some (~25-30%) patients in the HeFH study who may have higher than the target exposure (4000-9000 ng^{*} hr/ml) to MGL-3196 at the 100 mg dose. A few patients (10%) (likely to be non-LDL responders) may have drug levels lower than the target exposure. Therefore, the trial design is adaptive to optimize both safety and efficacy. Randomization will be 2:1, 100 mg MGL-3196 to placebo. The drug level of MGL-3196 reaches steady state in a few days. At the Week 2 clinic visit, an assessment of MGL-3196 PK will be performed, including measurement of the pre-dose and T_{max} (4 h) levels of MGL-3196. These two assessments will allow an accurate assessment of MGL-3196's total exposure. Between weeks 2-4, pending results of the PK measurements, all patients randomized to drug will be treated with 60 mg of MGL-3196. Based on the C_{max} value of MGL-3196 at Week 2, an unblinded clinical pharmacologist will assign MGL-3196 dose to the time period, Weeks 4-12. At Week 4, patients who had a Week 2 $C_{max} \geq 1500$ ng/ml will continue on 60 mg of MGL-3196 and those with $C_{max} < 1500$ ng/ml will be placed back on 100 mg/day.

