5 STUDY TREATMENTS

5.1 Treatment Groups

Patients who qualify for study inclusion will initially be randomized (2:1) to receive once-daily MGL-3196 100 mg or once-daily matching placebo given orally in the morning. All patients randomized to MGL-3196 will initially receive 100 mg QD through the week 2 visit, then 60 mg QD until the week 4 visit. At the week 4 visit, patients receiving MGL-3196 will be placed back on 100 mg if their week 2 MGL-3196 level 4 h postdose is < 1,500 ng/mL and described as the “100 mg group”; if the level of MGL-3196 \geq 1500 ng/ml they will continue to receive 60 mg QD for weeks 4-12 and will be described as the “60 mg group”. In summary, the assigned treatment groups are as follows:

- Placebo
- “100 mg group”: patients administered MGL-3196 100 mg for weeks 1-2, 60mg between week 2-4 visits, and 100 mg for weeks 4-12
- “60 mg group”: patients administered MGL-3196 100 mg for weeks 1-2 and 60 mg for weeks 2-12

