4. SAMPLE SIZE DETERMINATION

Up to 105 patients in total will be randomized to 1 of 2 treatments (70 patients to MGL-3196, 35 patients to placebo). It is estimated that the treatment difference of percent change in LDL-C from baseline to Week 12 between any dose of MGL-3196 group and the placebo group is about -20%. With a common standard deviation for the change in LDL-C at 20%, 27

patients per group to complete the Week 12 visit will provide 90% power with a two-sample t-test. The significance level is set as 0.025 for the consideration of multiplicity in comparisons of 2 daily dosing regimens of MGL-3196 vs. placebo group. The enrollment size is designed to allow for dropouts before the 12-week visit, and as such, patients who drop out of the study will not be replaced.

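### The 90% power statement assumes equal dose groups of 27, but dose-group size is set by the Week 2 drug level; for 60 mg versus placebo, power is about 76-90% if 25-30% of patients stay on 60 mg

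*Protocol*

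**What the plan says.** Protocol 10.2.4 sets out the enrolment: "Up to 105 patients in total will be randomized to 1 of 2 treatments (70 patient to MGL-3196, 35 patients to placebo". It assumes that the difference "between any dose of the MGL-3196 group and the placebo group is about -20" percent, adds "With a common standard deviation for the change in LDL-C at 20" percent, and concludes that "27 patients per group to complete the Week 12 visit will provide 90% power with a two-sample t-test". On alpha it says: "The significance level is set as 0.025 for the consideration of multiplicity in comparisons of 2 daily dosing regimens". The Synopsis carries the same text, and SAP 4 repeats the claim ("patients per group to complete the Week 12 visit will provide 90% power"). Enrolment is said to allow for dropouts, but no rate is given.

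The dose groups are not randomised. Under Protocol 5.1, "patients receiving MGL-3196 will be placed back on 100 mg if their week 2 MGL-3196 level 4 h postdose" is below 1,500 ng/mL; otherwise they stay on 60 mg for Weeks 4-12. Neither document states an expected split or a minimum size for the 60 mg group. The nearest figure is in Protocol 1.2.2, where exposure variability "may occur in some (~25-30%) patients in the HeFH study who may have higher than the target exposure" of 4000-9000 ng*hr/mL at 100 mg.

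The two documents differ on the primary comparison. Protocol 10.2.1.1 compares each dose group with placebo, with Dunnett's test, in the ITT Population with LOCF. SAP 2.1.1 keeps the two-group primary objective, but the primary model in SAP 3.7.2 has one pooled MGL-3196 group against placebo. Final dose appears in SAP 3.7.3, among subgroup analyses that are called descriptive and carry no multiplicity adjustment.

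**The concern.** The calculation is built for three groups of fixed, equal size. The design fixes only two sizes, 70 and 35. How the 70 divide is an outcome of the trial, so nobody can plan for 27 in each dose group; it can only be assumed, and the assumption is not stated. The one figure in the protocol that bears on the split points to a 60 mg group well below half of the active arm.

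Under the protocol's primary analysis, a non-significant 60 mg result would be read against a promised 90% power (type II error about 9% by exact calculation). If the 60 mg group is small, the type II error could be 20-24%. In the SAP, the sample size section justifies comparisons that the SAP does not make primary, so its reader is not told the power of the test that will be run.

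**Working it through.** **Inputs from Protocol 10.2.4.** Difference 20 points; SD 20 points, so the standardised difference is 1; alpha 0.025 per comparison; 27 completers per group; 70 and 35 randomised. Sidedness is not stated, and two-sided is assumed because it reproduces the stated figure (one-sided 0.025 would give 95.0%).

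**Formula.** For groups of n1 and n2, df = n1 + n2 − 2, the noncentrality is λ = 1/√(1/n1 + 1/n2), and power is the probability that a noncentral t with (df, λ) exceeds the two-sided critical value in absolute size.

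**Step 1: the stated figure.** 27 v 27: λ = 1/√(2/27) = 3.674, df = 52, critical value 2.308, power 91.0%. With 26 v 26 it is 89.8%, so 27 is the smallest equal group that reaches 90%. The arithmetic is right for equal groups.

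**Step 2: what equal groups require.** 3 × 27 = 81 completers, 81/105 = 77%, a loss of about 23%. This rate is back-calculated (27/35 gives the same). It leaves 54 active completers, so both dose groups have 27 only at an exact 50:50 split. With 27 on placebo, 90% power needs at least 26 on 60 mg (26 v 27 = 90.4%; 25 v 27 = 89.8%), which is 26/54 = 48% of active completers.

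**Step 3: power at a 25-30% share on 60 mg.** Two assumptions enter. The share above target exposure stands in for the share at or above 1,500 ng/mL, and loss is equal across groups. Group sizes are rounded to whole patients.

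| Loss | Placebo | Active | On 60 mg (25-30%) | Power, 60 mg v placebo |
|---|---|---|---|---|
| 23% | 27 | 54 | 14-16 | 75.7-79.7% |
| 10% | 32 | 63 | 16-19 | 82.5-86.9% |
| None | 35 | 70 | 18-21 | 86.9-90.3% |

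For example, 14 v 27: λ = 1/√(1/14 + 1/27) = 3.036, df = 39, critical value 2.331, power 75.7%. Rounding 13.5 down to 13 instead gives 73.3%, and 17.5 v 35 unrounded gives 86.2%. With 35 on placebo, 90% needs 21 on 60 mg, which is 30% of 70. So within this range 90% is reached only at a 30% share with no loss.

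**Step 4: other shares and the other comparisons.**
- 40% share on 60 mg: 22 v 27 = 87.4% (23% loss); 28 v 35 = 94.7% (no loss).
- 100 mg v placebo at a 25-30% share on 60 mg: 38-40 v 27 = 95.1-95.5%; 49-52 v 35 = 98.6-98.8%.
- Pooled MGL-3196 v placebo, 54 v 27: λ = 4.243, df = 79, power 97.3% at 0.025 and 98.7% at 0.05.

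**Step 5: Dunnett instead of 0.025 per test.** A simulated Dunnett critical value with pooled variance gives 78.1% (14 on 60 mg) to 81.8% (16) with 27 on placebo, and 88.3% (18) to 91.4% (21) with 35. The method adds about one to two points and does not remove the gap.

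**The case against.** The strongest reply is that the sentence is conditional and correct: if 27 per group complete, power is 90%. That stands. The fault is an unstated allocation assumption, not a wrong sum.

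A reader might infer that the protocol's own 25-30% figure fixes the 60 mg power at 76-80%. The documents do not support that, for two reasons. First, the range also needs the 23% loss, which neither document states. The protocol's primary analysis is ITT with LOCF, so the analysed numbers could approach 70 and 35, and power then rises to 87-90%. Second, 25-30% refers to an AUC range, while dose assignment uses a 4-hour level of 1,500 ng/mL, and no section links the two. It is the only high-exposure share that the documents give, but it remains a proxy.

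A reader might also ask how likely 27 of the 70 are to land on 60 mg and find only 0.8-7.8%. That sets a completer target against a no-dropout denominator. If all 105 are analysed, 21 on 60 mg suffice, with probability 20-54% over the same shares.

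Finally, the SAP's primary test is pooled and well powered, and its final-dose analysis is descriptive. That limits the consequence: the shortfall bears on the protocol's primary analysis and the SAP's final-dose analysis. It does not rescue the text of SAP 4, which still quotes a figure for a different set of comparisons.

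**Conclusion.** The point holds as a moderate one. The single 90% figure describes each dose comparison only if active completers split equally or nearly so, and the design neither fixes nor predicts such a split. At a 25-30% share on 60 mg, power for 60 mg versus placebo is about 76-90%, depending mainly on how many patients are lost from the analysis; the 100 mg comparison has about 95% or more. A share of 40% would put the 60 mg comparison at 87-95%.

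These figures rest on the protocol's difference and SD of 20, two-sided 0.025, equal loss across groups, and the exposure proxy. They do not show that the trial as a whole is underpowered. The SAP's pooled primary test has about 97% at 0.025 and 99% at 0.05 with 54 v 27.

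**What to change.** In Protocol 10.2.4 and the Synopsis, replace the single 90% statement with the power of each dose comparison. Say that dose-group size follows from the Week 2 level, and give the assumed 60 mg share with its basis, the dropout rate, the analysed numbers and the alpha with its sidedness. Show the 60 mg power as a range, about 76-90% for a 25-30% share, with the loss assumed at each end. If the sponsor holds data on the share expected at or above 1,500 ng/mL, that share should replace the proxy.

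In SAP 4, state the power of the pooled primary test and the alpha at which it is made, and give the final-dose comparisons separately with the same stated assumptions.

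The cost is wording in two protocol places and one SAP section, and one stated figure becomes less favourable. Enrolment, dosing and conduct do not change.

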11 DATA MANAGEMENT AND RECORD KEEPING

11.1 Data Management

11.1.1 Data Handling

Data will be recorded at the site on eCRFs and reviewed by the clinical research associate (CRA) during monitoring visits. The CRAs will verify data recorded in the EDC system with source documents. All corrections or changes made to any study data must be appropriately tracked in an audit trail in the EDC system. An eCRF will be considered complete when all missing, incorrect, and/or inconsistent data has been accounted for.

11.1.2 Computer Systems

Data will be processed using a validated computer system conforming to regulatory requirements.

11.1.3 Data Entry

Data must be recorded using the EDC system as the study is in progress. All site personnel must log into the system using their secure user name and password in order to enter, review, or correct study data. These procedures must comply with Title 21 of the Code of Federal Regulations (21 CFR Part 11) and other appropriate international regulations. All passwords will be strictly confidential.

11.1.4 Medical Information Coding

For medical information, the following thesauri will be used:

- Latest version of MedDRA for adverse events and medical history, and
- WHO Drug Dictionary for prior and concomitant medications.

11.1.5 Data Validation

Validation checks programmed within the EDC system, as well as supplemental validation performed via review of the downloaded data, will be applied to the data in order to ensure accurate, consistent, and reliable data. Data identified as erroneous, or data that are missing, will be referred to the investigative site for resolution through data queries.

The eCRFs must be reviewed and electronically signed by the Investigator.

11.2 Record Keeping

Records of patients, source documents, monitoring visit logs, eCRFs, inventory of study product, regulatory documents, and other Sponsor correspondence pertaining to the study must be kept in the appropriate study files at the site. Source data is defined as all information in original records and certified copies of original records of clinical findings, observations, or other activities in a clinical study necessary for the evaluation and reconstruction of the clinical study. Source data are contained in source documents (original records or certified copies). These records will be retained in a secure file for the period as set forth in the Clinical Study Agreement. Prior to transfer or destruction of these records, the Sponsor must be notified in writing and be given the opportunity to further store such records.

12 INVESTIGATOR REQUIREMENTS AND QUALITY CONTROL

12.1 Ethical Conduct of the Study

Good Clinical Practice (GCP) is an international ethical and scientific quality standard for designing, conducting, recording, and reporting studies that involve human patients. Compliance with this standard provides public assurance that the rights, safety, and well-being of study patients are protected, consistent with the principles that have their origin in the Declaration of Helsinki, and that the clinical study data are credible.

12.2 Institutional Review Board/Independent Ethics Committee

The IRB/IEC will review all appropriate study documentation in order to safeguard the rights, safety, and well-being of patients. The study will only be conducted at sites where IRB/IEC approval has been obtained. The protocol, Investigator's Brochure, Informed Consent Form (ICF), advertisements (if applicable), written information given to the patients, safety updates, annual progress reports, and any revisions to these documents will be provided to the IRB/IEC by the Investigator.

Federal regulations and ICH require that approval be obtained from an IRB/IEC prior to participation of patients in research studies. Prior to study onset, the protocol, any protocol amendments, ICFs, advertisements to be used for patient recruitment, and any other written information regarding this study to be provided to a patient or patient's legal guardian must be approved by the IRB/IEC.

No drug will be released to the site for dosing until written IRB/IEC authorization has been received by the Sponsor.

For study sites in Europe, it is the responsibility of the Sponsor or their designee (ie, [REDACTED]) to obtain the approval of the responsible IEC according to the national regulations. The study will only start in these sites once the respective committee's written approval has been given.

12.3 Informed Consent

The ICF and any changes to the ICF made during the course of the study must be agreed to by the Sponsor or designee and the IRB/IEC prior to its use and must be in compliance with all ICH GCP, local regulatory requirements, and legal requirements.

The Investigator must ensure that each study patient is fully informed about the nature and objectives of the study and possible risks associated with participation and must ensure that the patient has been informed of his/her rights to privacy. The Investigator will obtain written informed consent from each patient before any study-specific activity is performed and should document in the source documentation that consent was obtained prior to enrollment in the study. The original signed copy of the ICF must be maintained by the Investigator and is subject to inspection by a representative of the Sponsor, their representatives, auditors, the IRB/IEC, and/or regulatory agencies. A copy of the signed ICF will be given to the patient.

12.4 Patient Card

On enrollment in the study, European patients will receive a patient card to be carried at all times. The patient card will state that the patient is participating in a clinical research study, type of treatment, number of treatment packs received, and contact details in case of an SAE.

12.5 Study Monitoring Requirements

It is the responsibility of the Investigator to ensure that the study is conducted in accordance with the protocol, Declaration of Helsinki, Directive 2001/20/EC, ICH GCP, and applicable regulatory requirements, and that valid data are entered into the eCRFs.

To achieve this objective, the study monitor's duties are to aid the Investigator and, at the same time, the Sponsor in the maintenance of complete, legible, well organized and easily retrievable data. Before the enrollment of any patient in this study, the Sponsor or their designee will review with the Investigator and site personnel the following documents: protocol, Investigator's Brochure, eCRFs and procedures for their completion, informed consent process, and the procedure for reporting SAEs.

The Investigator will permit the Sponsor or their designee to monitor the study as frequently as deemed necessary to determine that data recording and protocol adherence are satisfactory. During the monitoring visits, information recorded on the eCRFs will be verified against source documents and requests for clarification or correction may be made. After the eCRF data is entered by the site, the CRA will review the data for safety information, completeness, accuracy, and logical consistency. Computer programs that identify data inconsistencies may be used to help monitor the clinical study. If necessary, requests for clarification or correction will be sent to Investigators. The Investigator and his/her staff will be expected to cooperate with the monitor and provide any missing information, whenever possible.

All monitoring activities will be reported and archived. In addition, monitoring visits will be documented at the investigational site by signature and date on the study-specific monitoring log.

12.6 Disclosure of Data

Data generated by this study must be available for inspection by the FDA, the Sponsor or their designee, applicable foreign health authorities, and the IRB/IEC, as appropriate. Patients or their legal representatives may request their medical information be given to their personal physician or other appropriate medical personnel responsible for their welfare.

Patient medical information obtained during the study is confidential and disclosure to third parties other than those noted above is prohibited.

12.7 Retention of Records

To enable evaluations and/or audits from regulatory authorities or the Sponsor, the Investigator will keep records, including the identity of all participating patients (sufficient information to link records, eg, eCRFs and hospital records), all original signed ICFs, copies of all eCRFs, SAE forms, source documents, and detailed records of treatment disposition. The records should be retained by the Investigator according to specifications in the ICH guidelines, local regulations, or as specified in the Clinical Study Agreement, whichever is longer. The Investigator must

obtain written permission from the Sponsor before disposing of any records, even if retention requirements have been met.

If the Investigator relocates, retires, or for any reason withdraws from the study, the Sponsor should be prospectively notified. The study records must be transferred to an acceptable designee, such as another Investigator, another institution, or to the Sponsor.

12.8 Publication Policy

Following completion of the study, the data may be considered for publication in a scientific journal or for reporting at a scientific meeting. Each Investigator is obligated to keep data pertaining to the study confidential. The Investigator must consult with the Sponsor before any study data are submitted for publication. The Sponsor reserves the right to deny publication rights until mutual agreement on the content, format, interpretation of data in the manuscript, and journal selected for publication are achieved.

12.9 Financial Disclosure

Investigators are required to provide financial disclosure information to the Sponsor to permit the Sponsor to fulfill its obligations under 21 CFR §54. In addition, Investigators must commit to promptly updating this information if any relevant changes occur during the study and for a period of 1 year after the completion of the study.

12.10 Insurance and Indemnity

In accordance with the relevant national regulations, the Sponsor has taken out patient liability insurance for all patients who have given their consent to the clinical study. This cover is designed for the event that a fatality, physical injury, or damage to health occurs during the clinical study's execution.

